13.4 Stratification Factors

Stratum 1: Patients with progressive unresectable or recurrent craniopharyngiomas treated with surgery alone, who have not received radiation therapy.

Stratum 2: Patients with progressive or recurrent craniopharyngiomas following radiation therapy.

13.4.1 Definition of Evaluable Patients

In both strata, all patients who receive at least 1 dose of PEGINTERFERON ALFA-2B will be considered evaluable for the purposes of assessing the primary objectives of this trial.

In both strata, patients who withdraw, are lost to follow-up, and/or are removed from treatment and who fail to be evaluated for the primary outcome will be counted as failures.

REFERENCES

- **2.** Rubinstein LJ RD. *Pathology of Tumours of the Nervous System.* 5 ed. Baltimore: Williams & Wilkie; 1990.

APPENDIX A Karnofsky/Lansky PERFORMANCE STATUS

The Karnofsky Scale is designed for recipients aged 16 years and older, and the Lansky Scale is designed for recipients less than 16 years old. Use the table below to determine the score (10-100) that best represents the recipient's activity status at the requested time point.

Table 1. Karnofsky/Lansky Scale

| Table 1. Karnorsky/Lansky Scale | | | | | |
|--|---|---|--|--|--|
| Karnofsky Scale (recipient age ≥ 16 years) | | Lansky Scale (recipient age <16 years) | | | |
| Able to carry on normal activity; no special care is needed | | Able to carry on normal activity; no special care is needed | | | |
| 100 | Normal, no complaints, no evidence of disease | 100 | Fully active | | |
| 90 | Able to carry on normal activity | 90 | Minor restriction in physically strenuous play | | |
| 80 | Normal activity with effort | 80 | Restricted in strenuous play, tires more easily, otherwise active | | |
| Unable to work, able to live at home cares for most personal needs, a varying amount of assistance is needed | | | Mild to moderate restriction | | |
| 70 | Cares for self, unable to carry on normal activity or to do active work | 70 | Both greater restrictions of, and less time spent in active play | | |
| 60 | Requires occasional assistance but is able to care for most needs | 60 | Ambulatory up to 50% of time, limited active play with assistance/supervision | | |
| 50 | Requires considerable assistance and frequent medical care | 50 | Considerable assistance required for any active play, fully able to engage in quiet play | | |
| Unable to care for self, requires equivalent of institutional or hospital care, disease may be progressing rapidly | | | Moderate to severe restriction | | |
| 40 | Disabled, requires special care and assistance | 40 | Able to initiate quite activities | | |
| 30 | Severely disabled, hospitalization indicated, although death not imminent | 30 | Needs considerable assistance for quiet activity | | |
| 20 | Very sick, hospitalization necessary | 20 | Limited to very passive activity initiated by others (e.g., TV) | | |
| 10 | Moribund, fatal process progressing rapidly | 10 | Completely disabled, not even passive play | | |

APPENDIX B Instructions for Administration of Subcutaneous Injections

Subcutaneous injections are given beneath the skin and not in a muscle. For small children, two persons may be needed. One holds and distracts the child and the other gives the injection. Before the injection is given, EMLA cream or ice can be applied to numb the area.

You will need:

- Alcohol swabs
- Syringe and needles
- Medication vial (powder)
- Diluent vial (liquid)
- Band-Aid

Procedure for Preparing the Medication:

- Select an area away from food and pets.
- Gather all of the equipment
- Wash your hands
- Open the syringe
- Clean the top of the vials (bottles) with alcohol
- Remove the cap from the syringe. Do not touch the needle.
- Pull back the plunger and fill the syringe with 0.7cc of air. Put the needle into the diluent (liquid) vial, and inject the air.
- Repeat the step above for the vial with the medicine (powder)
- With the tip of the needle in the vial with the liquid, turn the vial upside down and pull the plunger back to fill the syringe with 0.7 cc of the liquid. (Remember to keep the needle below the level of liquid).
- Remove the syringe and needle from the vial.
- Hold the syringe upright and tap on the sides to remove any air bubbles from the syringe.
- Push the plunger gently to remove bubbles.
- Recheck the syringe to make sure there is 0.7 cc of liquid.
- With the tip of the needle in the vial with the powder push the plunger and inject the liquid into the vial.
- Swirl the vial, do not shake, until the powder is dissolved. When the powder is completely dissolved it will be clear, colorless and without particles.
- After the powder is dissolved, clean the vial with an alcohol swab again.
- Take the second syringe, pull back the plunger and fill the syringe with the amount of air that is the same as your prescribed dose.
- With the tip of the needle in the vial, turn the vial upside down and pull the plunger back to fill the syringe with the cc amount of your prescribed dose. (Remember to keep the needle below the level of liquid).
- Hold the syringe upright and tap on the sides to remove any air bubbles from the syringe.
- Push the plunger gently to remove bubbles.
- Recheck the syringe to make sure there is the correct amount of cc in the syringe.

• Replace the cap loosely onto the syringe.

Procedure for Giving the Medication:

- Remove clothing from the injection site
- Clean the injection area with alcohol using a circular motion. Start in the center and move outward.
- Let the skin air dry.
- Remove the cap from the needle.
- Grasp and raise the skin ½ to 1 inch.
- Insert the needle into the skin with a quick darting motion at a 45-90 degree angle.
- Release your grasp on the skin.
- Pull back the plunger and check for any blood in the syringe.
- If there is blood, remove the needle from the skin and begin again using a new needle.
- If there is no blood, push the plunger slowly until the syringe is empty.
- Remove the syringe quickly from the skin.
- If necessary, put a Band-Aid over the injection site.
- Make sure to throw the syringe into a puncture resistant container.
- Keep a record on your medication diary.

Storage: SYLATRON (PEGINTERFERON ALFA-2B) should be stored at 25°C, excursions permitted to 15-30°C. Do not freeze. Keep away from heat. After reconstitution with supplied diluent, the solution should be used immediately, but may be stored up to 24 hours at 2 to 8°C. However it is recommended that the solution be used within 3 hours after mixing. The reconstituted solution contains no preservative, is clear and colorless.

.

APPENDIX C SYLATRON (PEGINTERFERON ALFA-2B) Dosage Calculation and Chart

Dosage calculation:

The total dose of SYLATRON is calculated based on subject weight. The following formula should be used to calculate the dose:

Dose in mL = Weight (kg) x Dose ("X" μ /kg)

Reconstituted Vial Strength (μ /ml)

Note: Vials are available in 200 mcg per 0.5 mL

Example

Vial Strength= $200 \mu g/0.5 mL$ ($400 \mu g/ml$) Subject Weight=60 kg

Dose in mL= $60 \text{ kg x } 1.0 \quad \mu\text{g/kg}$

400 μg/mL

Dose = 0.15 mL SYLATRON

Weight 20 kg to 120 kg (patients with weights less than 20 kg are ineligible)

| | | Volume to be | | |
|----------------|-----------------|----------------|--------------------|--|
| Weight | Dosage Strength | administered | Dose to administer | |
| (Kilogram, Kg) | | subcutaneously | | |
| 20 | 200 mcg/0.5ml | 0.05 ml | 20 mcg | |
| 24 | 200 mcg/0.5ml | 0.06 ml | 24 mcg | |
| 28 | 200 mcg/0.5ml | 0.07 ml | 28 mcg | |
| 32 | 200 mcg/0.5ml | 0.08 ml | 32 mcg | |
| 36 | 200 mcg/0.5ml | 0.09 ml | 36 mcg | |
| 40 | 200 mcg/0.5ml | 0.1 ml | 40 mcg | |
| 44 | 200 mcg/0.5ml | 0.11 ml | 44 mcg | |
| 48 | 200 mcg/0.5ml | 0.12 ml | 48 mcg | |
| 52 | 200 mcg/0.5ml | 0.13 ml | 52 mcg | |
| 56 | 200 mcg/0.5ml | 0.14 ml | 56 mcg | |
| 60 | 200 mcg/0.5ml | 0.15 ml | 60 mcg | |
| 64 | 200 mcg/0.5ml | 0.16 ml | 64 mcg | |

^{*} Reconstitute vial with 0.7 ml and use no more than 0.5 ml from each vial.

| 68 | 200 mcg/0.5ml | 0.17 ml | 68 mcg |
|-----|---------------|---------|---------|
| 72 | 200 mcg/0.5ml | 0.18 ml | 72 mcg |
| 76 | 200 mcg/0.5ml | 0.19 ml | 76 mcg |
| 80 | 200 mcg/0.5ml | 0.2 ml | 80 mcg |
| 84 | 200 mcg/0.5ml | 0.21 ml | 84 mcg |
| 88 | 200 mcg/0.5ml | 0.22 ml | 88 mcg |
| 92 | 200 mcg/0.5ml | 0.23 ml | 92 mcg |
| 96 | 200 mcg/0.5ml | 0.24 ml | 96 mcg |
| 100 | 200 mcg/0.5ml | 0.25 ml | 100 mcg |
| 104 | 200 mcg/0.5ml | 0.26 ml | 104 mcg |
| 108 | 200 mcg/0.5ml | 0.27 ml | 108 mcg |
| 112 | 200 mcg/0.5ml | 0.28 ml | 112 mcg |
| 116 | 200 mcg/0.5ml | 0.29 ml | 116 mcg |
| 120 | 200 mcg/0.5ml | 0.3 ml | 120 mcg |

APPENDIX D Stress-Dose Steroid Dosing

Suggested stress-dose steroid dosing for patients on physiologic replacement hydrocortisone

- If the patient develops fever between 38-40 degrees Celsius without vomiting within 72 hours of a dose of PEGINTERFERON ALFA-2B, the next dose of hydrocortisone should be doubled.
- If the patient develops fever > 40 degrees Celsius without vomiting within 72 hours of a dose of PEGINTERFERON ALFA-2B, the next dose of hydrocortisone should be tripled.
- If the patient develops vomiting or poor perfusion and is not able to tolerate PO meds, 100 mg IM hydrocortisone should be administered.

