Based on this, a Phase II study of alpha-interferon was performed in pediatric patients with progressive or recurrent craniopharyngiomas. 15 Interferon alpha-2a was administered subcutaneously daily for 16 weeks followed by a 32 week maintenance phase where the interferon was given three times/week. Three of 12 evaluable patients showed a minor response (n=1), partial response (n=1) or complete response (n=1); the patient with the PR also showed improvement in visual fields. The median time to progression was 25 months (range 3-37+ months with 3 patients without progression as of last follow-up). The cystic component of the tumor often increased temporarily during the first several months of treatment. Toxicities requiring temporary discontinuation and/or dose reduction were common during the initial 16 weeks of therapy. All patients developed fever shortly after receiving the first dose of IFN, usually accompanied by chills and myalgias. Two patients with panhypopituitarism developed hypotension and lethargy during the fever, requiring stress dose steroids. discontinuation and/or dose reduction was required for toxicity in nine (60%) of the 15 patients during the first 8 weeks of treatment but resolved after temporary discontinuation and/or dose reduction. These toxicities included worsening seizures, transaminase elevations, rash and anorexia/weight loss.

Intralesional interferon-alpha has also shown efficacy against craniopharyngiomas. In a multicenter study, 60 patients with predominantly cystic craniopharyngiomas were treated with every other day intra-cystic interferon-alpha. Forty-seven (78%) of the 60 patients had a > 50%

decrease in the size of the cyst.¹⁶ A separate study of 8 patients with cystic craniopharyngiomas treated with intra-cystic alpha-interferon showed an increase in the apoptotic factor soluble FasL concentrations in the cyst fluid of all 8 patients as the cyst decreased in size in response to treatment, suggesting that interferon works by inducing Fas-mediated apoptosis.¹⁷

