2.2.3 Rationale for PEGINTERFERON ALFA-2B Dose

Although interferon-alpha has been used to treat a variety of neoplasms, the optimal dose in oncology has not been established. In vivo studies have not shown a clear dose-response relationship in solid tumors, other than possibly for melanoma²⁴. In CML, low dose interferon is just as effective as higher doses²⁵ whereas toxicity is clearly dose-related.

A Phase I study of PegIntron alpha-2b in pediatric patients with neurofibromatosis-related plexiform neurofibromas has recently been published.²⁶ The recommended Phase 2 dose (RP2D) was 1 mcg/kg/week with fatigue and intolerable behavioral toxicities seen at higher doses. There was only one DLT (myoclonus) in 12 patients treated at the RP2D. This toxicity had not been seen previously and was felt to be possibly related, although it continued intermittently even after the drug was discontinued. Only 1 other patient required a dose reduction for grade 3 elevation of transaminases. This dose is also the FDA approved dose for the treatment of hepatitis C in adults when used as monotherapy. Although a higher dose of PEGINTERFERON ALFA-2B is used in adult patients with melanoma, where there is a known dose-response curve, a dose of 1 mcg/kg/week resulted in a prolonged CR in one of the patients in the pilot study.²⁷

Many, if not most patients with craniopharyngiomas have panhypopituitarism and require stress doses of steroids to remain hemodynamically stable in the face of high fever and/or chills, which are common dose-related side effects of interferon, and almost universally seen with higher doses, particularly with short acting interferon. A dose of 1 mcg/kg/week has been found to be well tolerated in pediatric patients²⁶, causing only mild to moderate constitutional symptoms which subside over time, and has shown efficacy in the pilot study at Children's Hospital of Pittsburgh.²⁷ Therefore, a dose of 1 mcg/kg/week will be utilized for all patients in this protocol, regardless of age.

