5.1 Agent Administration

SYLATRON will be administered as a weekly subcutaneous injection for up to 18 courses with 6 injections per course. Six consecutive weeks will constitute one course and subsequent courses will immediately follow, with no break in the administration of the drug. All patients will receive a dose of 1 mcg/kg/week. The patient's actual weight (in kilograms) should be used when calculating the dose of SYLATRON and doses should be re-adjusted if necessary at the time of each clinic evaluation. See Appendix C for the SYLATRON dosage calculation and dosage chart. Patients or parents will be taught to administer the medication in the outpatient setting (see Appendix B for a parent handout on administering subcutaneous injections). Patients or their guardians will keep a diary to document SYLATRON administration (available on the PBTC-039 webpage).

Since constitutional symptoms (e.g., fatigue, myalgias, fever) are generally the most severe after the first few doses, acetaminophen (15 mg/kg up to max dose of 1000 mg) should be given 30 minutes prior to administering the first six doses (first course) of SYLATRON and prior to subsequent doses if needed. For fever that develops after a dose of SYLATRON, Acetaminophen (15 mg/kg up to max dose of 650 mg PO) can be given q 4-6 hours as needed, but should not exceed 75 mg/kg/day for a total dose of up to 3000 mg/day. Acetaminophen can also be alternated with ibuprofen (10 mg/kg up to a max dose of 600 mg) every 6-8 hours as needed. Patients who are on replacement steroids for adrenal insufficiency should receive stress dose steroids for any fever > 101 degrees Fahrenheit (38.3 degrees Centigrade). Please see Appendix D for suggested stress steroid dosing for SYLATRON related fever.

It is recommended that a follow-up call be placed to the patient or parent within 72 hours of the first dose to evaluate for toxicities and review optimal management.

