7.1 Adverse Events and Potential Risks

7.1.1 Adverse Event List(s) for SYLATRON (Peginterferon alfa-2b). See package insert for further information.

COMMON, SOME MAY BE SERIOUS

In 100 people receiving Peginterferon alfa-2b, more than 20 and up to 100 may have:

- Nausea, vomiting, loss of appetite
- Chills, fever
- Reaction during or following injection of the drug which may cause fever, chills, rash, low blood pressure
- Swelling and redness at the site of the medication injection
- Tiredness
- Pain
- Dizziness, headache
- Depression
- Hair loss
- Liver damage which may cause belly pain

OCCASIONAL, SOME MAY BE SERIOUS

In 100 people receiving Peginterferon alfa-2b, from 4 to 20 may have:

- Anemia which may require blood transfusions
- Abnormal heartbeat which may cause fainting
- Heart attack or heart failure which may cause shortness of breath, swelling of ankles, cough or tiredness
- Bleeding of the eye
- Bruising, bleeding
- Confusion
- Change in personality
- Sensing things that are not there
- State of mind that involves a "loss of contact with reality"
- Thoughts of suicide or harming others
- Low blood pressure

RARE, AND SERIOUS

In 100 people receiving Peginterferon alfa-2b, 3 or fewer may have:

- Blood clot
- Blurred vision with chance of blindness

Adverse Event Characteristics

CTCAE term (AE description) and grade: The descriptions and grading scales found in the revised NCI Common Terminology Criteria for Adverse Events (CTCAE) version 4.0 will be utilized for recording AEs in the RDC database. The descriptions and grading scales found in the revised NCI Common Terminology Criteria for Adverse Events (CTCAE) version 4.0 will be utilized until March 31, 2018 for expedited AE reporting. CTCAE version 5.0 will be utilized for expedited AE reporting beginning April 1, 2018. All appropriate treatment areas should have access to a copy of the CTCAE versions 4.0 and 5.0. A copy of the CTCAE **CTEP** 4.0 5.0 downloaded from the versions and can be web site http://ctep.cancer.gov/protocolDevelopment/electronic applications/ctc.htm.

Attribution of the AE:

- Definite The AE *is clearly related* to the study treatment.
- Probable The AE *is likely related* to the study treatment.
- Possible The AE *may be related* to the study treatment.
- Unlikely The AE *is doubtfully related* to the study treatment.
- Unrelated The AE *is clearly NOT related* to the study treatment.

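### Appendix D ties the intramuscular hydrocortisone step for poor perfusion to oral intolerance, so a febrile, poorly perfused, non-vomiting patient judged able to tolerate oral medicine is pointed only to a larger next dose

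*Combined protocol and SAP*

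**What the plan says.** Section 5.1 (Agent Administration) says that patients on replacement steroids for adrenal insufficiency should receive stress-dose steroids for fever above 38.3 °C. For the dosing it directs: "Please see Appendix D for suggested stress steroid dosing for SYLATRON related fever".

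Appendix D is headed "Suggested stress-dose steroid dosing for patients on physiologic replacement hydrocortisone" and has three bullets:

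- Bullet 1: for "fever between 38-40 degrees Celsius without vomiting within 72 hours of a dose of PEGINTERFERON ALFA-2B, the next dose of hydrocortisone should be doubled".
- Bullet 2: above 40 °C, under the same two conditions (no vomiting, within 72 hours of a dose), the next dose is tripled.
- Bullet 3: "If the patient develops vomiting or poor perfusion and is not able to tolerate PO meds, 100 mg IM hydrocortisone should be administered".

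Bullets 1 and 2 exclude vomiting but do not mention perfusion. Bullet 3 is the only place where perfusion appears, and the only parenteral steroid step in the document.

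**The concern.** Naming poor perfusion in bullet 3 suggests that the authors saw it as a reason to inject. As worded, it has no force unless oral medicine also fails. The written suggestion for a steroid-dependent patient with signs of circulatory compromise is then the same as for a patient with fever alone. It acts through the next scheduled dose and does not say to bring that dose forward.

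The protocol itself makes the situation foreseeable:

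- Section 2.2.3 says that many, if not most, of these patients have panhypopituitarism and "require stress doses of steroids to remain hemodynamically stable in the face of high fever and/or chills".
- Section 2.2.1, on the earlier interferon study, reports: "Two patients with panhypopituitarism developed hypotension and lethargy during the fever, requiring stress dose steroids".
- Section 7.1 lists among the common events "Reaction during or following injection of the drug which may cause fever, chills, rash, low blood pressure". Low blood pressure also appears there on its own, as occasional (4 to 20 in 100).
- Section 5.1 has patients or parents give the injections as outpatients, so a reaction may begin with no clinician present.

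What is at stake is patient safety in an urgent but uncommon case. No estimate or test in the trial depends on it.

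**Working it through.** There is no plan figure to reproduce. The check treats the three bullets of Appendix D as decision rules and runs them over every case.

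**Inputs.** The three bullets above, for a patient on replacement hydrocortisone with fever within 72 hours of a dose. V = vomiting, P = poor perfusion, O = oral medicine tolerated (1 = yes, 0 = no). *Raise* means that the next dose is doubled (38–40 °C) or tripled (above 40 °C). *IM* means 100 mg intramuscular hydrocortisone.

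**Rules.**

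- Bullets 1 and 2, current and proposed: raise if V = 0.
- Bullet 3, reading A: IM if (V or P) and not O.
- Bullet 3, reading B: IM if V or (P and not O).
- Bullet 3 with *or* in place of *and*: IM if V or P or not O.

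**The case in question** is V = 0, P = 1, O = 1.

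- Reading A: (no or yes) and no = not met.
- Reading B: no or (yes and no) = not met.
- Bullet 1 or 2: V = 0, so met. Result: raise only.
- A well-perfused patient (V = 0, P = 0, O = 1) gets the same result: raise only.
- With *or*: no or yes or no = met. Result: raise and IM.

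**All eight cases.**

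| V | P | O | Current, reading A | Current, reading B | With *or* |
|---|---|---|---|---|---|
| 0 | 0 | 1 | raise | raise | raise |
| 0 | 0 | 0 | raise | raise | raise + IM |
| 0 | 1 | 1 | raise | raise | raise + IM |
| 0 | 1 | 0 | raise + IM | raise + IM | raise + IM |
| 1 | 0 | 1 | none | IM | IM |
| 1 | 0 | 0 | IM | IM | IM |
| 1 | 1 | 1 | none | IM | IM |
| 1 | 1 | 0 | IM | IM | IM |

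With *or*, two cases change on both readings (0-0-0 and 0-1-1). Two change on reading A only (1-0-1 and 1-1-1), and four do not change: 2 + 2 + 4 = 8. All four rows with P = 1 and all four with O = 0 now include IM. No row loses a step on either reading. These are logical cases and say nothing about how often each occurs.

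**Is there a rule elsewhere?** Section 5.1 sets the fever threshold and refers to Appendix D. It has no rule on perfusion or hypotension. The dose-modification rules in Section 6 concern peginterferon. No other section gives a parenteral steroid step.

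**The case against.** Several points on the other side stand.

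- **It is guidance.** Section 5.1 and Appendix D both call the dosing suggested, and a clinician may give parenteral steroid regardless. A reader might infer that the protocol withholds or forbids the injection in a poorly perfused patient. The text does not support that.
- **Tolerance is undefined.** Tolerating oral medicine is not the same as being able to swallow it, and a clinician may well judge that a poorly perfused patient does not tolerate it. The gap exists only where poor perfusion is recognised and oral medicine is still judged tolerated.
- **Harm is not shown.** A reader might take the two patients in the earlier study as evidence that a raised oral dose is inadequate. The text gives neither dose nor route for their steroids, and that study used daily non-pegylated interferon. It shows that hypotension during fever occurs, not that oral dosing fails. Section 2.2.3 expects only mild to moderate constitutional symptoms at 1 mcg/kg/week, so the case should be less common here.
- **There is some safety net.** The patient still gets a doubled or tripled dose, and Section 5.1 recommends a call within 72 hours of the first dose.

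Bullet 3 could also be a deliberate rule about route: oral if tolerated, injection if not. The documents do not exclude this. But on that account oral intolerance alone would be enough, and the mention of poor perfusion would add nothing. As written, a non-vomiting, well-perfused patient who cannot take oral medicine gets no injection on either reading (case 0-0-0). So the wording does not deliver that rule either.

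**Conclusion.** The point holds as a gap in suggested safety wording. On both readings of bullet 3, the febrile, poorly perfused, non-vomiting patient judged able to tolerate oral medicine is pointed to the same step as a well-perfused patient, and nothing elsewhere corrects this. Its size is one of eight logical cases. The documents give no frequency, and none is estimated.

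The conclusion assumes that the bullets are followed as written. It also assumes that bullet 3, which does not repeat the fever and 72-hour conditions, is read in the setting that Section 5.1 gives it, fever related to the study drug.

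It is a cheap improvement for patient safety. Design, endpoints, data and sample size are untouched.

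**What to change.** In bullet 3 of Appendix D, replace the *and* that introduces the clause on oral tolerance with *or*, preceded by a comma. Vomiting, poor perfusion and oral intolerance then become three alternative triggers for the 100 mg injection. Leave bullets 1 and 2 and all dose amounts as they are.

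The clinical team should confirm the wording and two consequences:

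- A patient who vomits but still tolerates oral medicine is now clearly directed to the injection, which is today's reading B. A narrower edit that freed only poor perfusion from the oral condition, and kept that condition for vomiting, would leave this patient with no step.
- A non-vomiting patient who meets bullet 3 also meets bullet 1 or 2, as case 0-1-0 does now. The team may wish to say whether the raised next dose still follows the injection.

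The cost is one word and a notice to sites, plus some additional injections, including in patients who vomit or are poorly perfused but could have taken oral medicine.
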